Fatigue is a common debilitating symptom in neurological disorders, and over 50% of Parkinson's disease (PD) patients report fatigue as one of their top three debilitating symptoms. The definitions of fatigue are subjective, but they all focus on having an abnormal lack of energy that interferes with normal function [2]. Currently, there are no evidence-based guidelines for treating fatigue in PD, and no effective medications or therapeutic modalities exist for fatigue symptoms in patients with PD. Multiple medications are being tried with no evidence in double-blind clinical trials. One study showed a statistically significant improvement with methylphenidate, but no effect was seen when data from other stimulant trials were pooled. A post hoc analysis of rasagiline showed statistically but clinically insignificant improvements, and levodopa showed small benefits for fatigue. However, non-motor symptoms were not the primary endpoints of the study, and further research is required to better understand and treat fatigue in PD. We hypothesize that fatigue is due to diminished levels of norepinephrine in PD. The locus coeruleus (LC), one of the major sources of norepinephrine, is affected during the preclinical phase of PD during stage 2 of Braak pathology staging. Norepinephrine is the final metabolite of dopamine, and we hypothesize that by adding exogenous norepinephrine, we can control some of the motor and non-motor symptoms of Parkinsonism. Norepinephrine is the final metabolite of droxidopa, and it is still unclear if it passes the blood-brain barrier. Here, we propose a pilot study to explore our hypotheses and to measure the efficacy and safety of droxidopa in Parkinsonism patients with fatigue.

Scientific Value:

Randomized control studies addressing fatigue in patients with Parkinsonism are an insufficiently addressed requirement to understand how to improve quality of life outcome measures. The lack of progress in understanding the pathophysiology and treatment of fatigue, along with the absence of effective therapy for fatigue in patients with Parkinsonism argues for a greater effort. The goal of the proposed pilot study is to follow patients over 6 months total (with 3 months of it being an open-label trial). The outcomes of our study will help determine the efficacy of droxidopa for fatigue in patients with Parkinsonism. Additionally, the outcomes of our study will provide us important information regarding the efficacy of droxidopa on other non-motor and motor symptoms of Parkinsonism.

Primary Product:

Droxidopa

(Droxidopa is also known as L-threo-3,4-dihydroxyphenylserine, or L-DOPS. Droxidopa is decarboxylated by 3,4-dihydroxyphenylalanine (DOPA) decarboxylase (DDC), and is directly converted to Nor Epinephrine. There are four stereoisomers of L-DOPS; however, only the L-threo-enantiomer (droxidopa) is biologically active. It is the International Non-proprietary Name (INN) for a synthetic amino acid precursor of NE, which was originally developed by Sumitomo Dainippon Pharmaceuticals Co., Limited, Japan (SDP). It has been approved for use in Japan since 1989 and in the United States (US) since February 2014).

Safety Profile

Droxidopa is safe and well tolerated in patients with symptomatic Neurogenic Orthostatic Hypotension associated with primary autonomic failure (PD, MSA and PAF), Dopamine Beta Hydroxylase Deficiency, or Non Diabetic Autonomic Neuropathy. Data from this program indicates that droxidopa treatment is associated with a small increase in supine hypertension (SBP >180 mmHg), and an increase in the incidence of headaches, dizziness, and nausea. Data from the SDP-sponsored clinical studies conducted in Europe and the large safety database of patients treated in Japan, where droxidopa has been marketed for over 20 years, further support the safety of droxidopa. Community standards do not require lab work, including pregnancy tests, when initiating or maintaining therapy with Droxidopa.

Primary Study Objective:

- To determine the efficacy of droxidopa for fatigue in patients with Parkinsonism measured by the Visual Analog Fatigue Scale (VAFS).

Table 1 (on Page 7 of this protocol) describes how the study will be conducted. This is a randomized, placebo-controlled, double-blind clinical trial for 3 months, and after a wash-out period of 7 days, every subject will receive droxidopa for another 3 months during the open-label phase. This approach will provide us with the chance to evaluate the efficacy of droxidopa for as long as 6 months. There will be one follow up visit that occurs 4 weeks after the final 6 month visit when Droxidopa has been withdrawn to evaluate fatigue in the absence of droxidopa. Subjects who meet the inclusion/exclusion criteria and consent to participating in the study will be randomized to the experimental group (droxidopa treatment for the entire 6 months) or control group (placebo for first 3 months then droxidopa treatment for the remaining 3 months) by a random number generator. Subjects and the Principal Investigator/ Sub Investigator will be blinded to the group allocation for the first 3 months of the study. During the first 3 months of the double-blind phase, both groups will titrate (either droxidopa for the experimental group or placebo for the control group) then continue their optimal dose for 3 months. After a 7-day wash-out period, both groups will titrate again (droxidopa only this time), then continue their optimal dose for another 3 months during the open-label phase.

We will perform detailed assessments (see table 1) for the primary and secondary efficacy outcomes at 6 different visits, including the first screening/ baseline visit.

Visit 1 will be screening/ baseline visit, where informed consent and demographics will be taken, it will also include a complete physical examination and vitals along with orthostatic standing test will also be taken. History of intake of concomitant medications, prohibited medications, and recent diagnostic, therapeutic or surgical procedures, will be taken. Medications taken in the 28 days prior to study will be recorded. It will be

during this visit that the droxidopa or placebo will be distributed and the titration will begin. VAFS and UPDRS will be completed at this visit.

Visit 2 will occur 6 weeks from screening, and medication titration will finish prior to this day. History of intake of concomitant medications, any adverse events, physical exam, vital signs, adherence to treatment regimen including avoidance of prohibited medications, and recent diagnostic, therapeutic or surgical procedures, will be recorded and VAFS and UPDRS will be completed. IMP will be dispensed and compliance and capsule count will be done on this visit and remaining IMP will be returned.

Visit 3 will occur 6 weeks from Visit 2 and correspond with the maintenance period. Again history of intake of concomitant medications, any adverse events, physical exam, vital signs, adherence to treatment regimen including avoidance of prohibited medications, and recent diagnostic, therapeutic or surgical procedures will be recorded, and VAFS and UPDRS will be completed. Compliance and capsule count will be done on this visit too and remaining IMP will be returned. Patients will be instructed to stop taking their IMP following this visit and IMP will be not be dispensed.

Visit 4 will occur 1 week from Visit 3 and will begin the open-label titration. The patients will not be taking IMP for 7 days (plus 0-14 days) prior to visit 4 to create a washout period. Again history of intake of concomitant medications, any adverse events, physical exam, vital signs, adherence to treatment regimen including avoidance of prohibited medications, and recent diagnostic, therapeutic or surgical procedures will be recorded and VAFS and UPDRS will be completed. IMP (droxidopa only, no placebo) will be distributed and the titration will begin.

Visit 5 will occur 6 weeks from Visit 4 and will and medication titration will finish prior to this day. History of intake of concomitant medications, any adverse events, physical exam, vital signs, adherence to treatment regimen including avoidance of prohibited medications, and recent diagnostic, therapeutic or surgical procedures, will be recorded and VAFS and UPDRS will be completed. IMP will be dispensed and compliance and capsule count will be done on this visit and remaining IMP will be returned.

Visit 6 will occur 6 weeks after Visit 5 and will correspond with the maintenance period. Again history of intake of concomitant medications, any adverse events, physical exam, vital signs, adherence to treatment regimen including avoidance of prohibited medications, and recent diagnostic, therapeutic or surgical procedures will be recorded, and VAFS and UPDRS will be completed. Compliance and capsule count will be done on this visit too and remaining IMP will be returned. Patients will be instructed to stop taking their IMP following this visit and IMP will be not be dispensed.

Visit 7 will be final visit which will happen 4 weeks after visit 6 to evaluate fatigue in the absence of droxidopa. History of intake of concomitant medications, any adverse events, physical exam, vital signs, and recent diagnostic, therapeutic or surgical procedures, will be recorded, and VAFS and UPDRS will be completed at this visit.

Table 1

Study Procedure	Visit 1	Visit 2	Visit 3	Visit 4	Visit 5	Visit 6	Visit 7
	Screening/ Baseline	Double blinded Titration	Double blinded Maintenance	Washout	Open-Label Titration	Open-Label Maintenance	Final Visit
Interval	Time 0	6 weeks (+ 0-14 days)	6 Weeks (+ 0-14 days)	1 week (+ 0-14 days)	6 Weeks (+0-14 days days)	6 Weeks (+0-14 days days)	4 Weeks (+0-14 days days)
Time from Baseline	Time 0	6 weeks from baseline	12 weeks from baseline	13 weeks from baseline	16 weeks from baseline	25 weeks from baseline	29 weeks from baseline
Written Informed consent	X						
Review inclusion and exclusion criteria	X						
Demography	X						
Concomitant medication	X	x	X	x	X	X	X
Adverse events (continuous monitoring)		x	X	x	X	X	X
Physical examination	X	x	X	x	X	X	X
Vital signs (BP, HR, RR, temp) and weight	X	x	X	x	X	X	X
Orthostatic Standing Test	x						
Dose titration evaluation		x			x		
VAFS	x	x	X	x	X	X	X
UPDRS	x	x	X	x	X	X	X
Randomization	x						
Unblinding			x				
Blinding	x						
IMP dispensed	x	x		x	x		
Capsule count / compliance check		x	X		x	x	
IMP returned		x	x		x	x	

Use of Concomitant, Prior, and Prohibited Medications

• Concomitant Medications

No prescribed concomitant medication is to be taken without the knowledge of the Investigator. The Investigator may, at their discretion, prescribe any medication considered necessary for the patient's welfare that is not expected to interfere with the evaluation of the IMP. All concomitant medications must be recorded. The generic name of the drug, dose, frequency of dose and the duration of treatment must be specified. In addition, any diagnostic, therapeutic or surgical procedure conducted during the study, that is not part of the study, should be recorded. The date, indication, description of procedure(s) and any clinical finding should be recorded.

All concomitant medications should be maintained at stable doses during the study. If patients are already on other concomitant medications, which based on investigator judgment, would be expected to have side effect of hypertension, (e.g, amphetamine, amphetamine-like drugs, serotonin-norepinephrine reuptake inhibitors (SNRIs), and norepinephrine reuptake inhibitors (NRIs), evaluate their continued use when introducing droxidopa.

• Prior Medications

Prior medication includes all medications (including herbal treatments and vitamins) taken within 28 days prior the Screening Visit . All prior medications taken within 28 days of the Screening Visit must be recorded.

• Prohibited Medications

Administering droxidopa in combination with other agents that increase blood pressure (e.g, norepinephrine, ephedrine, midodrine, triptans) would be expected to increase the risk for supine hypertension. The following drugs must not be prescribed by the Investigator or taken by patients during the study:

- Vasoconstricting agents such as ephedrine, dihydroergotamine, or midodrine;
- Sumatriptan-like drugs, (for example, naratriptan, zolmitriptan, rizatriptan);
- Cyclopropane or halothane, or other halogen-containing inhalational anesthetics;
- Catecholamine-containing preparations (e.g. isoprenaline);
- Non-selective monoamine oxidase inhibitors (MAOIs) including linezolid;
- Ergotamine derivatives (except if anti-Parkinsonian medication);
- Drugs that have anti-hypertensive properties and, in the Investigator's opinion, significantly contribute to the patient's orthostatic hypotension; and
- Any investigational medication.

Patients currently taking a prohibited medication at Screening may be enrolled into the study after a washout of at least 5 half-lives prior to first dose of IMP.

Inclusion Criteria (All Patients)

1. Age of 50 years or older.
2. Clinical diagnosis of Parkinsons Disease or Atypical Parkinsonism (including MSA, PSP)
3. Patients should be fluent and be able to understand and converse freely in English.
4. Patient should report fatigue as a symptom and must have a mean VAFS score of 4 or more at baseline.
5. Provide written informed consent to participate in the study and understand that they may withdraw their consent at any time without prejudice to their future medical care.

Exclusion Criteria (All Patients)

1. In the Investigator's opinion, the patient is not able to understand or cooperate with study procedures.
2. Known or suspected alcohol or substance use disorder within the past 12 months (as per DSM-5 criteria)
3. Women who are pregnant or breastfeeding
4. Women of childbearing potential (WOCP)
5. Sustained supine hypertension greater than or equal to 180 mmHg systolic or 110 mmHg diastolic. Sustained is defined as the average of 3 observations each at least 10 minutes apart with the patient having been supine and at rest for at least 5 minutes prior to each measurement.
6. Untreated closed angle glaucoma
7. Diagnosis of hypertension that requires treatment with antihypertensive medications
8. Any significant uncontrolled cardiac arrhythmia.
9. History of myocardial infarction, within the past 2 years.
10. Current unstable angina.
11. Congestive heart failure (NYHA Class 3 or 4).
12. Diabetic autonomic neuropathy.

13. History of cancer within the past 2 years other than a successfully treated, non-metastatic cutaneous squamous cell or basal cell carcinoma or cervical cancer in situ.
14. Gastrointestinal condition that may affect the absorption of Investigational Medicinal Product (e.g. ulcerative colitis, gastric bypass).
15. Any major surgical procedure within 30 days prior to the first titration visit.
16. Currently receiving any investigational drug or have received an investigational drug within 28 days prior to the first titration visit.
17. Any condition or laboratory test result, which in the Investigator's judgment, might result in an increased risk to the patient, or would affect their participation in the study.
18. The Investigator has the direction to exclude a patient if, for any reason, they feel the patient is not a good candidate for the study or will not be able to follow study procedures.
19. We will also exclude patients with dementia or non-treated depression, because fatigue may be associated with these conditions, and these patients may be less reliable at completing assessments and with medication compliance.
20. Subjects who have a mean VAFS score of less than 4 at baseline will be excluded from the study.
21. We will exclude vulnerable populations from this study.
22. Patients with uncontrolled intercurrent illnesses including, but not limited to severe lung disease, ongoing or active infection, symptomatic congestive heart failure, unstable angina pectoris, symptomatic cardiac arrhythmia, and situations that would limit compliance with study requirements will be excluded.
23. Orthostatic hypotension (OH) will be excluded from this study.

Exit Criteria

Patients will be removed from the study if the patient has any side effects, or the patient feels uncomfortable continuing the study for any reason or physician feels patient is not safe to continue study.

Early Termination Visit

If at any time during the study a patient requests to withdraw from treatment, or if a decision is made to withdraw the patient, the patient will be requested to return for an

early termination visit. A decision will be made to withdraw the patient from the study while on site due to non-adherence to the plan as detailed in the protocol, the development of any adverse effects, the development of any of the above stated exclusion criteria, or due to starting any of the prohibited medications for this study. The early termination procedures should be completed during that visit. The patient should not be brought back for an Early Termination Visit at a later date.

Whenever practical, patients should be encouraged to remain on IMP until the completion of the early termination procedures. This is particularly important for patients who withdraw from the study during the double-blind treatment period. As the primary efficacy endpoint is time to intervention, it is critical that the date of withdrawal (which will be the date of the patient's last dose) due to a need for intervention during the double-blind period is accurately recorded.

The Investigator or qualified designee will conduct the following procedures and record the data.

- Record the time and dose of IMP taken on the day of the visit
- Record the reason for withdrawal
- Review of AEs
- Review of concomitant medication

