Patients with AEs must be treated in accordance with usual clinical practice at the discretion of the Investigator. Non-serious AEs must be followed up until resolution or the follow-up assessment whichever comes first. At the safety follow-up visit information on new SAEs, if any and stop dates for previously reported AEs must be recorded. It is the responsibility of the Investigator to follow up on SAEs until the patient has recovered, stabilized, or recovered with sequelae, and to report to Lundbeck all relevant new information using the same procedures and timelines as those for the initial report. Relevant information includes discharge summaries, autopsy reports, and medical consultations. SAEs that are spontaneously reported by a patient to the Investigator after the follow-up assessment must be handled in the same manner as SAEs that occur during the study. These SAEs will be captured in the Global Pharmacovigilance database.

Informed Consent

It is the responsibility of the Investigator to obtain written informed consent from each patient participating in this study, after adequate explanation of the aims, methods, potential benefits and any potential hazards of the study. No study-related procedures, including washout of any medications, may be performed prior to obtaining written informed consent.

The Investigator must explain that the patients are completely free to refuse to enter the study or to withdraw from it at any time and for any reason. Similarly, the Investigator or Lundbeck is free to withdraw the patient from the study at any time for safety reasons. Any other requirements necessary for the protection of the human rights of the patient will also be explained.

Confidentiality

All patients who provide written informed consent will be assigned a patient number. Subsequently, patients will be identified in the records only by their initials, date of birth, and their patient number (as allowed by local country regulations). Any information published as a result of the study will be such that it will not permit identification of any patient. The information from this study will be available within Lundbeck and may be shared with regulatory authorities. It may also be the subject of an audit by a regulatory agency, such as the Food and Drug Administration (FDA), within the local government. The patient's identity will remain protected except as required for legal or regulatory inquiries.

Data Collection

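### The schedule leaves no time for the prohibited-drug washout: consent, baseline fatigue rating, randomisation and start of study drug share Visit 1, and washout may not precede consent

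*Protocol*

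**What the plan says.** Four parts of the protocol bear on the point.

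- **Prohibited Medications.** A patient on a prohibited drug at Screening "may be enrolled into the study after a washout of at least 5 half-lives prior to first dose of IMP". The same section explains that combining droxidopa with other pressor agents is expected to raise the risk of supine hypertension.
- **Informed Consent.** "No study-related procedures, including washout of any medications, may be performed prior to obtaining written informed consent".
- **Study Method/Design, Visit 1.** "Visit 1 will be screening/ baseline visit, where informed consent and demographics will be taken". It is also "during this visit that the droxidopa or placebo will be distributed and the titration will begin", and the VAFS and UPDRS are completed at the same visit.
- **Table 1.** Consent, eligibility review, VAFS, UPDRS, randomisation, blinding and the first dispensing of study drug (IMP) are all marked at Visit 1, Time 0. Visit 2 follows six weeks later.

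The Visit 1 VAFS has two uses. Inclusion criterion 4 and exclusion criterion 20 set a threshold of 4 on it for entry. The Statistics section adjusts the comparison of change scores for the randomisation value.

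A related pair of statements stands under Concomitant Medications: "All concomitant medications should be maintained at stable doses during the study". For drugs expected to raise blood pressure, such as stimulants, SNRIs and NRIs, the investigator is to "evaluate their continued use when introducing droxidopa".

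**The concern.** The washout has a fixed earliest start (consent) and a fixed latest end (first dose), and the schedule puts both at the same visit. A site that wants to enrol such a patient has no route that complies with every statement.

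Two things are at stake. The first is the safeguard itself: if titration begins at Visit 1 as written, the prohibited drug has not been washed out. The second is the baseline. If the first dose is delayed instead, the Visit 1 VAFS has already been rated in a drug state that is about to end. Any effect of stopping the drug then enters the change from baseline together with the effect of study treatment, and the eligibility decision rests on a fatigue level that may no longer apply. Adjusting for baseline does not remove a shift that happens after baseline.

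The stable-dose statement raises a lesser question of timing. Doses are to stay constant during the study, while the continued use of certain drugs is to be reviewed as droxidopa is introduced. The protocol does not say whether that review comes before or after the baseline rating.

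**Working it through.** No sample size or power figure is involved. The check is a comparison of times, followed by a simple bound on size.

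**Inputs**

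- Earliest start of washout: written consent (Informed Consent). Consent is at Visit 1, Time 0 (Study Method/Design; Table 1).
- Scheduled start of IMP: Visit 1, Time 0 (Study Method/Design; Table 1).
- Required washout: at least 5 half-lives before the first dose (Prohibited Medications).
- Next visit: six weeks after Visit 1, so no visit lies between consent and first dispensing.
- Group size: 16 per arm, 32 in total (Study Method/Design).
- Number of patients on a prohibited drug, and any VAFS change on stopping it: not given.

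**Time available**

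Scheduled start of IMP − earliest start of washout = 0 − 0 = 0 days. Five half-lives exceed 0 days for any drug, so the washout cannot fit.

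**What a site could do**

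1. *Begin titration at Visit 1 as scheduled.* The washout rule is broken.
2. *Begin washout before Visit 1.* The consent rule is broken.
3. *Hold back the first dose after Visit 1.* The start of titration departs from the schedule, and the Visit 1 VAFS and randomisation already precede the washout.
4. *Spread Visit 1 over several days, with the ratings and randomisation after the washout.* This would satisfy the washout and consent rules, but the protocol does not describe it. The only washout interval in Table 1 is the IMP washout between Visits 3 and 4.

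**Size**

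Let k patients in one arm each shift by d points after baseline because a prohibited drug was stopped. Their baseline values do not change, so the arm's mean change moves by k × d / 16.

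- k = 1, d = 1: 1/16 = 0.0625, about 0.06 points.
- k = 4, d = 1: 4/16 = 0.25 points.

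Both k and d are assumptions. If m patients in the other arm shift equally, the arm difference moves by (k − m) × d / 16. Under random allocation with equal arms, k − m has expectation zero.

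**The case against.** The strongest reply is that the protocol does not actually prescribe a baseline taken on the old drug. It says that these patients are enrolled after the washout, and the ANCOVA covariate is the value at randomisation. A sensible site could take consent, wait, and then do the ratings and randomise. This is fair as an account of what was probably intended. It does not remove the conflict, because the text and Table 1 fix all these steps at one Time 0 visit and give no interval for it.

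The second reply is that few patients are concerned. This stands. Exclusion criteria 7 (treated hypertension), 16 (recent investigational drug), 22 (active infection and other uncontrolled illness) and 23 (orthostatic hypotension) already remove many likely users of the listed drugs.

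A reader might infer more than the document supports:

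- *That the treatment comparison is biased.* Randomisation affects both arms alike on average. What remains is added noise and chance imbalance in small arms. Nor does the protocol say that any prohibited drug alters fatigue.
- *That the same impossibility applies to stimulants, SNRIs and NRIs.* They are not on the prohibited list, the washout rule does not reach them, and a review of continued use need not change a dose. That is a question of timing only.
- *That the wording "prior to the first titration visit" in exclusion criteria 15 and 16 proves a separate screening visit was dropped.* The criteria do not say the visit is separate, and titration begins at Visit 1, so the phrase can refer to Visit 1.

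**Conclusion.** The contradiction is certain from the text: the washout rule, the consent rule and the single-visit schedule cannot all be met for a patient on a prohibited drug at Screening. It belongs to the protocol, since consent order, visit timing and eligibility are not matters that a statistical analysis plan would settle.

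Its numerical effect is modest: about 0.06 points on an arm mean for each affected patient who shifts by 1 point, without a predictable direction. That figure rests on an assumed shift, and the number of such patients is unknown. The case for correction rests mainly on the lack of a compliant path, the loss of a stated safeguard and, for these patients, the blurred meaning of baseline and eligibility. The change should be made, but this is not a threat to the trial's main comparison.

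**What to change.** Reconcile Study Method/Design (Visit 1), Table 1, Prohibited Medications and Informed Consent. One way is a Table 1 footnote: for patients who need a prohibited-drug washout, consent and screening are separated from baseline, and the eligibility and baseline VAFS and UPDRS, randomisation and dispensing follow completion of the washout. All other patients keep the single Visit 1.

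Separately, reconcile the two statements under Concomitant Medications by saying how the review of continued use is timed relative to baseline and to the stable-dose requirement. No view is taken here on which drugs should be stopped, continued or washed out, or for how long.

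The cost is protocol wording and a footnote, plus one extra attendance and a short delay for the probably few patients concerned.

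### The orthostatic hypotension exclusion conflicts with the prohibited-drug washout rule, and as scheduled the only standing test and the baseline VAFS come before that washout

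*Protocol*

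**What the plan says.** Exclusion Criteria (All Patients), item 23, reads "Orthostatic hypotension (OH) will be excluded from this study". It gives no blood-pressure definition, no time of assessment and no rationale.

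The Prohibited Medications section lists, among others, "Vasoconstricting agents such as ephedrine, dihydroergotamine, or midodrine" and "Drugs that have anti-hypertensive properties and, in the Investigator's opinion, significantly contribute to the patient's orthostatic hypotension". It then states: "Patients currently taking a prohibited medication at Screening may be enrolled into the study after a washout of at least 5 half-lives", counted back from the first dose of study drug. That sentence does not refer to exclusion 23.

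The Informed Consent section rules out any study procedure, medication washout included, before written consent. The Visit 1 description in Study Method/Design places consent at that visit, with a "complete physical examination and vitals along with orthostatic standing test will also be taken". VAFS and UPDRS are completed there, study drug is handed out and titration starts. Table 1 marks consent, randomization and dispensing at Visit 1 and marks the orthostatic standing test at Visit 1 only. The Statistics section uses the value at randomization as the ANCOVA covariate.

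**The concern.** The second drug clause quoted above has its plain meaning only for a patient who has OH, yet item 23 says that no such patient should be in the trial. For a candidate with OH who takes such a drug, the two sections do not yield one clear answer. If the OH resolves off the drug, eligibility turns on whether item 23 is judged before or after the washout, and the protocol does not say.

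The pressor agents raise the opposite problem. A patient whose standing pressure is supported by one of them could have an unremarkable standing test at Visit 1, stop the agent, and start study drug with OH that nobody has formally looked for.

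Two things are at stake. Patients whom the protocol means to exclude may be enrolled. And a fatigue effect in such patients is harder to interpret: the Safety Profile section describes droxidopa's use in "symptomatic Neurogenic Orthostatic Hypotension associated with primary autonomic failure (PD, MSA and PAF"), two of which are diagnoses recruited here, while the hypothesis under test is that fatigue in PD reflects diminished norepinephrine.

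**Working it through.** No arithmetic applies: the protocol gives no OH frequency, no count of candidates on prohibited drugs and no effect of OH on VAFS. The check is to follow one candidate, taking a prohibited pressor agent at screening, through the protocol.

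1. **Consent.** It is obtained at Visit 1 (Visit 1 description; Table 1).
2. **Earliest washout.** It must follow consent (Informed Consent section), so it cannot start before Visit 1.
3. **Latest washout.** At least 5 half-lives must pass before the first dose (Prohibited Medications).
4. **Standing test.** It is marked once, at Visit 1 (Table 1). No repeat is called for after a washout.
5. **Baseline VAFS.** It is also taken at Visit 1. It serves as the ANCOVA covariate (Statistics) and as the entry threshold of 4 or more (inclusion 4, exclusion 20).
6. **Randomization and dispensing.** Both are at Visit 1. Table 1 has no visit between consent and dispensing.

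Steps 1 to 6 place the standing test and baseline VAFS at the consent visit, before the washout, while every follow-up VAFS is taken off the agent. Read literally, the schedule also cannot be completed in one sitting for this candidate, because the washout has to fit between consent and first dose. The protocol offers no split visit to accommodate it.

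A candidate on a blood-pressure-lowering drug meets the same sequence. Exclusion 7, "Diagnosis of hypertension that requires treatment with antihypertensive medications", narrows that route to drugs with such properties taken for another reason. It does not touch the pressor route.

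The later safeguards compare as follows.

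- **Withdrawal rule** (Early Termination Visit): a patient who develops an exclusion criterion is withdrawn, but no further standing test is scheduled that would show it.
- **UPDRS item 42**: asked at every visit, but it covers symptomatic orthostasis only.
- **UPDRS data form**: has lines for supine and standing pressure. The first use after Visit 1 is Visit 2, at 6 weeks plus 0 to 14 days (6 to 8 weeks), when titration is complete.
- **Vital signs in Table 1**: no posture is specified. At early termination the pressure is supine.

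All of these operate after dosing has begun, so none protects entry.

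**The case against.** The strongest reply is that eligibility criteria apply together. The washout sentence is permissive and lifts only the medication bar; nothing in it waives exclusion 23. A patient with manifest OH at Visit 1 is excluded whatever the drug history. Visit 1 also records concomitant, prohibited and prior medication, so a pressor agent would be seen, and a patient known to take it for OH already falls under item 23. Exclusions 17 and 18 give the investigator further discretion. The prohibited list also governs drugs taken during the study, so the OH clause is not purely an entry rule. All of this stands. A reader might infer that the protocol authorises an exception for patients with OH; it does not.

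A second reply is that the order of standing test and washout is left open rather than fixed wrongly. This stands in part. The protocol does not state the order in words, but a site following Table 1 would do the test at the consent visit, and nothing calls for it again.

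A third reply is that the harm is inferred. That is correct for the mechanism. The protocol does not say that OH causes fatigue, that droxidopa relieves fatigue through blood pressure, or why item 23 exists; exclusion 19, by contrast, gives its reason. A reader might also infer a biased comparison between arms. Randomization balances the entry of such patients in expectation, so a VAFS difference in them would be a real drug effect. The difficulty lies in what it would be taken to show.

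**Conclusion.** The point holds as a conflict in the text plus a gap in the schedule. The two sections need reconciling, and following Table 1 as written can leave exclusion 23 unenforced in a patient whose standing pressure depended on the stopped drug. In the same patients the baseline VAFS is taken under a different drug regimen from all follow-up.

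The size cannot be derived. One could assume 1 to 3 such patients per arm of 16 and a 2-point VAFS gap between treated and untreated OH, giving 2 × 1/16 = 0.125 to 2 × 3/16 = 0.375 points. Neither input has any anchor in the protocol, so this range is an illustration and the conclusion does not rest on it.

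The conclusion assumes only that at least one candidate takes a prohibited drug at screening and enters by the washout route. It matters for who is enrolled and for interpretation in a 32-patient pilot. It does not show that the primary comparison is invalid.

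**What to change.** 1. Reconcile the Prohibited Medications section with exclusion 23 so that together they give one answer for a candidate with OH who takes a prohibited drug, and state whether item 23 is judged before or after the washout. Which answer is right is a clinical decision for the sponsor and investigator; none is proposed here, nor any rule on stopping or starting these drugs.
2. For any patient who undergoes the washout, place the existing orthostatic standing test (read against exclusion 23) and the baseline VAFS after the washout and before randomization and first dose. Add a note to Table 1 that Visit 1 may be split for this purpose, with consent on the first day.

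No new assessment is introduced, and the analysis model is unchanged. The cost is protocol wording, a delayed or two-part Visit 1 for a few candidates, and possibly the loss of a few who prove ineligible on the later test or the later VAFS.
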